2. LAY SUMMARY

This research study is focused upon assessing and optimising surgeon's performance during, and patient outcomes following, total hip replacement (THR) surgery. The primary research question is to determine if additional simulation training can improve the intra-operative performance of surgical trainees (Specialty Registrars) during a THR, or the outcome of patients after their THR. We will also aim to define an 'expert' standard in performing a primary elective THR, which may be used as a benchmark when assessing surgical trainee performance; and also determine if operative surgeon performance metrics during a THR are correlated with surgical experience, or patient outcomes.

The surgeon participants in this study will be divided into 2 groups depending upon their position and seniority. The 'Expert' group will be composed of Consultant Orthopaedic Surgeons and Senior Fellows, and the 'Trainee' group will be composed of Trauma & Orthopaedic Specialty Registrars (StR's) on Deanery clinical placements. The intervention to be tested is the simulation-based training and cognitive learning package. This will be delivered for 1-2 hours per week over a 4-week period in a supervised non-clinical setting to a randomised sub-group of 50% of the Specialty Registrars enrolled into this study. Surgeon participants within the Expert group will not undergo any interventions.

The outcome measures will be surgeon-specific and patient-specific. These outcome measures for the 'Trainee' group will commence following completion of the simulation training (if applicable), whereas they can commence immediately following study approval for the 'Expert' group. The surgeon-specific outcome measures will be the objective motion-analysis metrics generated by validated and extensively used wireless sensors placed on the elbows of surgeons under their sterile gowns during the operation; and subjective assessments of surgical trainee performance using validated and reliable forms of structured human grading. Patient-specific outcome measures will be collected for a pre-determined number of patients who have undergone a primary elective THR by any of the surgeon participants in this study. All patient-specific outcome measures (with the exception of a post-operative questionnaire) are routinely collected as part of the patients NHS clinical care, and no other additional investigations are required for conducting this research. All patients will be asked to provide their written informed consent for the use of their data in this study. The patient-specific outcome measures include: pre- and post-operative blood tests and radiograph (X-ray) analysis; the incidence of blood transfusions and any other peri-operative complications; the in-patient length of stay; and two patient-reported outcome measure (PROMs) questionnaires.

Statistical analysis will then be performed on the data collected, specifically aiming to identify any significant differences in either surgeon performance metrics, or patient outcome measures between:

- 1) The StR's who have undertaken additional simulation training versus those who have routine Deanery training.
- 2) The 'Trainee' group and the 'Expert' group. A sub-group analysis may be performed within the 'Expert' group also to determine any differences between the Consultants and Fellows.

In summary, this novel research will use validated methodology and routinely collected patient outcome measures in order to determine the impact of simulation training on surgical trainee performance and patient outcomes following a primary elective THR, and also help to benchmark an expert level of performance in this commonly performed and highly effective operation. The results of this study will hopefully help in shaping the future of orthopaedic surgical training and assessment within the United Kingdom.

3. SYNOPSIS

Study Title	A prospective randomised controlled study assessing the impact of simulation training in primary total hip replacement (THR).
Short title	THR Performance & Assessment
Study registration	IRAS Project ID: 270167 6th August 2019
Sponsor	University of Oxford/Clinical Trials and Research Governance Joint Research Office, [name]

Funder	Dinwoodie Charitable Company		
Study Design	Prospective randomised controlled study, with an additional comparator group.		
Study Participants	
Trauma & Orthopaedic Specialty Registrars (intervention and control groups), Consultant Orthopaedic Surgeons, and Arthroplasty Fellows.
 
Patients undergoing elective primary THR at the 2 named NHS Hospitals in this study, when their lead surgeon is enrolled as a participant in this study.
		
Participant Sample Size	
Surgeon participant Group 1 a: Interventional group ('StR's'): Thames Valley Deanery Trauma & Orthopaedic Specialty Registrars on Arthroplasty clinical placements (n=8) receiving additional training
 
Surgeon participant Group 1 b: control group (StR's): Thames Valley Deanery Trauma & Orthopaedic Specialty Registrars on Arthroplasty clinical placements receiving routine and normal Deanery training only (n=8).
 
Surgeon participant Group 2: ('Experts & Fellows'): Consultant Orthopaedic Surgeons (n=5), and nationally appointed Arthroplasty Fellows (n=8).
 
Patient Participants: Estimated total n= 193, calculated on the basis of outcomes data following THR to be collected for:
 
 8 patients per Specialty Registrar (n = 128) 5 patients per Fellow (n = 40) 5 patients per Consultant (n = 25) 		
Planned Study Period	
Total length of project = 18-24 months
 
Length of individual participants involvement = 6 months
		
Planned Recruitment period	
Start date for recruitment = August 2019
 
End date for recruitment = February 2021 (with possible extension to August 2021)
		
	Objectives	Outcome Measures	Timepoint(s)
Primary	
To assess the impact of simulation training on surgical trainee performance and patient outcomes following THR.
	
Participants:
 
 • Wireless motion data metrics from elbow worn sensors (hand movements, path length and time taken). • Global Rating Scales (GRS). • Objective Structured Assessment of Technical Skills (OSATS). • Surgical checklists. 
Patients:
 
 • X-ray analysis of THR.[4] • Blood loss and transfusion rates. 	
Intra-operative assessments to be performed at a minimum of 8 separate THR operations for each participant in Group 1 (StR'S) over a 6-month period.
 
Outcome measures data will be collected for all patients who have had a THR performed by any participant as the

		
 • Peri-operative patient morbidity • In-patient length of stay. • PROMs: EQ-5D and OHS. 	lead surgeon in this study.
Secondary	
To define an expert standard when performing a primary elective THR.
 
To determine if operative surgeon performance metrics during a THR relate to surgical experience, or patient outcomes.
	
Participants:
 
 • Wireless motion data metrics from elbow worn sensors (hand movements, path length and time taken). 
Patients:
 
 • X-ray analysis of THR.[4] • Blood loss and transfusion rates. • Peri-operative patient morbidity • In-patient length of stay. • PROMs: EQ-5D and OHS. 	
Intra-operative assessments at a minimum of 5 separate THR operations for each participant in Group 2 (Experts & Fellows).
 
Outcome measures data will be collected for all patients who have had a THR performed by any participant as the lead surgeon.

Intervention(s)	The intervention to be tested is the simulation-based training and cognitive learning package. This will be delivered in a supervised non-clinical laboratory setting to a randomised sub-group of 50% of the participants within the 'StR' group.		

4. ABBREVIATIONS

AF's	Arthroplasty Fellows
CCT	Certificate of Completion of Training
CI	Chief Investigator
CTRG	Clinical Trials & Research Governance, University of Oxford
CUREC	Central University Research Ethics Committee
DGH	District General Hospital
EPR	Electronic Patient Record
EQ-5D	EuroQol-5D
GCP	Good Clinical Practice
GDPR	General Data Protection Regulation
GRS	Global Rating Scales
HRA	Health Research Authority
ICF	Informed Consent Form
LOS	Length of stay
MS-IDREC	Medical Sciences Inter-Divisional Research Ethics Committee

NDORMS	Nuffield Department of Orthopaedics, Rheumatology, and Musculoskeletal Sciences
NHS	National Health Service
NICE	National Institute for Health and Clinical Excellence
NJR	National Joint Registry
NOC	Nuffield Orthopaedic Centre
OHS	Oxford Hip Score
OOSEC	Oxford Orthopaedic Simulation & Education Centre
OPD	Out-Patient Department
OUH	Oxford University Hospitals
PACS	Picture Archiving and Communication System
PI	Principal Investigator
PIC	Participant Informed Consent
PIS	Participant Information Sheet
POAC	Pre-operative assessment clinic
PROMs	Patient-Reported Outcome Measures
PSA	Procedure-Specific Assessments
QALY	Quality-Adjusted Life Year
R&D	NHS Trust R&D Department
REC	Research Ethics Committee
RES	Research Ethics Service
SOP	Standard Operating Procedure
StR	Specialty Registrar
TMS	Theatre Management System
T&O	Trauma & Orthopaedic
THR	Total Hip Replacement
TSC	Training & Standards Committee
UTH	University Teaching Hospital
WGH	Wycombe General Hospital
WHO	World Health Organisation
W/L	Waiting Lists

5. BACKGROUND AND RATIONALE

THR is one of the most commonly performed, cost-effective, and successful orthopaedic operations of the 21st century. Since 2002, the NJR of England and Wales has recorded information on all patients and

implants used in arthroplasty (joint replacement) surgery, including THR, and report these figures annually (<http://www.njrcentre.org.uk>). According to the 15th annual NJR report in 2018, 91,698 primary (first time) THR's were performed in the year up to 31st December 2017. Furthermore, a total of 992,218 primary THR have been recorded on the NJR following its inception in 2002, which reflects the huge demand for this operation. According to the latest NJR annual report data, the mean age for a patient undergoing a primary THR is 68.0 (SD 11.4), with 59.8% females and 40.2% males. The most common indication for a patient to have a THR in the NHS is primary osteoarthritis of the hip joint, which accounted for 90% (n=86,994) of all THR cases recorded in the 15th annual NJR report.

This study builds upon previous research from our group, which has demonstrated the value of simulation training in arthroscopic orthopaedic surgery, and mini-open partial (uni-compartmental) knee replacement. This research proposal aims to utilise similar proven methodology and validated technology to evaluate and determine the effectiveness of simulation training in THR surgery, with the aim of improving training and patient outcomes. Defining an 'expert' surgeon standard in primary THR has never been attempted using motion analysis data. However, previous research from our group has used this technology and methodology to differentiate surgeons of various levels of training based upon their intra-operative performance metrics as measured by the wireless motion sensors. The accuracy, validity, and safety of these motion sensors has been proven in these previous research projects, and we now plan on utilising them in a commonly performed 'open' orthopaedic operation.

The reasons for undertaking this study are to improve training in THR surgery, and to make recommendations to the national orthopaedic training and standards committee. By delivering the above aims, we will be able to:

- 1) Determine if additional simulation-based training for surgical trainees leads to improved intra-operative performance, or patient outcomes following THR.
- 2) Define an expert standard when performing a primary elective THR. This information will be a useful 'benchmark' against which Surgical Trainees performance and competence can be measured.
- 3) Determine if operative surgeon performance metrics during a THR relate to surgical experience, or patient outcomes.

The justification for including an 'Expert' comparator group within our study is to establish a benchmark standard of the optimal surgical performance metrics for a primary THR, against which we can assess StR performance. Within this study we have combined the 'Experts' and 'Fellows' into a single group as all the participants within this group are post-CCT (certificate of completion of training) in Trauma & Orthopaedic Surgery, and will undertake the same assessments at the same time points. The 'Fellows' are eligible to apply for Consultant posts, and will therefore represent a sub-Consultant level of performance, which we anticipate to be higher than that of StR's, but potentially below that of an established Consultant. The reason we are recording performance data for both 'Experts' and 'Fellows', is that this will allow further sub-group analysis, which may identify differences in performance metrics or patient outcomes between these surgeons.

The simulation-based training (intervention) to be tested in this study has been granted ethical approval by the University of Oxford Medical Sciences Interdivisional Research Ethics Committee (Reference MS-IDREC R57808/RE001).

6. OBJECTIVES AND OUTCOME MEASURES

Objectives	Outcome Measures	Timepoints of evaluation
Primary To assess the impact of simulation training on surgical trainee performance and patient outcomes following THR.	Participants: 
 Wireless motion data metrics from elbow worn sensors (hand movements, path length and time taken) Global Rating Scales (GRS). Objective Structured Assessment of Technical Skills (OSATS). Surgical checklists. Patients: 
 X-ray analysis of THR.[4] Blood loss and transfusion rates. Peri-operative patient morbidity In-patient length of stay. PROMs: EQ-5D and OHS. 	Intra-operative assessments to be performed at a minimum of 8 separate THR operations for each participant in Group 1 (StR'S) over a 6-month period. Outcome measures data will be collected for all patients who have had a THR performed by any participant as the lead surgeon in this study.
Secondary To define an expert standard when performing a primary elective THR. To determine if operative surgeon performance metrics during a THR relate to surgical experience, or patient outcomes.	Participants: 
 Wireless motion data metrics from elbow worn sensors (hand movements, path length and time taken) Patients: 
 X-ray analysis of THR.[4] Blood loss and transfusion rates. Peri-operative patient morbidity In-patient length of stay. PROMs: EQ-5D and OHS. 	Intra-operative assessments at a minimum of 5 separate THR operations for each participant in Group 2 (Experts & Fellows). Outcome measures data will be collected for all patients who have had a THR performed by any participant as the lead surgeon.

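### The patient-outcome set is defined two ways, and no rule keeps registrars' pre-training operations out of the between-arm comparison

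*Combined protocol and SAP*

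**What the plan says.** **All patients, no start.** The primary row of section 6 says that patient outcome data are "collected for all patients who have had a THR performed by any participant as the lead surgeon in this study". The synopsis (section 3) repeats this. The patient inclusion criteria in section 8.2 require that the lead surgeon be a participant and say nothing about when the operation falls relative to training.

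**A fixed number, after training.** The lay summary (section 2) says "Patient-specific outcome measures will be collected for a pre-determined number of patients who have undergone a primary elective THR". Having described the outcome measures as both surgeon-specific and patient-specific, it adds: "These outcome measures for the 'Trainee' group will commence following completion of the simulation training (if applicable". The synopsis supplies the number: "8 patients per Specialty Registrar (n = 128", with "5 patients per Fellow (n = 40" and "5 patients per Consultant (n = 25" for the comparator group.

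**Timing of assessments only.** Section 7 starts each registrar's intra-operative assessments at week 6 of the placement, with at least 8 operations. Section 9.3 places the intervention arm's assessments after training, at about two every six weeks, 8 in total. Neither section says that patient outcomes are limited to those operations.

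**Analysis.** Section 11 compares outcomes between the registrar sub-groups and, within the intervention sub-group, before and after training. It does not say which patients enter which comparison.

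**The concern.** Patient outcomes belong to the primary objective, so the choice of patients affects every X-ray, haemoglobin, transfusion, morbidity, length-of-stay and PROM comparison between the registrar arms. Three things are left open.

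- A registrar is a participant from enrolment, before the course is delivered. Under section 6 a THR led by an intervention registrar during the training weeks is an intervention-arm outcome. Under the lay summary it is not.
- The section 11 before/after analysis needs exactly those early operations. Once they are collected, no rule separates them from the between-arm data.
- The lay summary's qualifier, if applicable, gives controls no start point. If controls counted from the start of the placement and intervention registrars only after training, the arms would be sampled at different stages of the placement, and experience gained on it would be mixed with the effect of simulation.

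Left unresolved, the set could be chosen after the data have been seen.

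**Working it through.** **1. The plan's own total.** Inputs from the synopsis: 16 registrars, 8 Fellows and 5 Consultants, with 8, 5 and 5 patients each.

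16 × 8 + 8 × 5 + 5 × 5 = 128 + 40 + 25 = 193

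This agrees with "Estimated total n= 193". At the lower recruitment figures in section 8.1 (12 registrars, 6 Fellows) it is 96 + 30 + 25 = 151. The sample size is therefore built on a fixed number per surgeon, not on every THR led.

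**2. Fit with the assessment schedule.** Two assessments at each of weeks 6, 12, 18 and 24 give 2 × 4 = 8. The 8 patients per registrar match 8 assessed operations from week 6, although no section states the link.

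**3. The two definitions side by side.**

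| | Start for registrars | Number | Control-arm start |
|---|---|---|---|
| Sections 3 (outcomes), 6, 8.2 | none given | all led by a participant | none given |
| Section 2, with the number from section 3 | after training | 8 per registrar | not defined |
| Sections 7, 9.3 (assessments only) | week 6 / after training | minimum of 8 / total 8 | week 6 (section 7) |
| Section 11, before/after analysis | needs operations before training | not given | not applicable |

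**4. Possible dilution under section 6.** The documents do not say how many THRs a registrar leads before training ends. Assumptions: a 6-month placement is 26 weeks; training starts in week 0; operations are spread evenly; all early patients are eligible and consented; an operation before completion shows no training effect. The course lasts w = 4 weeks (section 9.6) up to 6 weeks (section 7).

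Pre-training share f = w/26; retained arm difference = 1 − f.

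- w = 4: f = 4/26 = 15.4%; retained 84.6%
- w = 6: f = 6/26 = 23.1%; retained 76.9%

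These are upper figures. Fewer early cases, or some benefit from a part-completed course, would bring f or the loss down towards zero. If the set is only the assessed operations, f = 0.

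**5. What this would do to power.** The documents give no effect size, SD or intraclass correlation (ICC), so this is illustration only. Take 8 v 8 registrar means, non-central t with 14 df, two-sided 5%, and an assumed difference of 1.5 SD of a registrar mean based on 8 patients. Power without dilution is 80%.

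- Number held at 8 per registrar: the difference becomes 1.5 × 0.846 = 1.27 or 1.5 × 0.769 = 1.15, and power 66% or 57%.
- Early cases added to 8 later ones, which is what taking all patients implies: m = 8/(1 − f) = 9.5 or 10.4 per registrar. The SD of a registrar mean is multiplied by √{[ρ + (1 − ρ)/m] / [ρ + (1 − ρ)/8]}. With ICC ρ = 0.05 the factor is 0.944 or 0.915, the standardised difference 1.34 or 1.26, and power 71% or 65%. With ρ = 0.20 power is 68% or 61%.

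The extra patients therefore recover part of the loss.

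**The case against.** The best reply is that the documents can be read consistently. The lay summary gives a timing rule covering patient outcomes, and section 6 is silent on the start rather than opposed to it. Section 6 speaks of collecting data, which is not the same as entering every patient in the arm comparison. Patients enter only after screening and consent, so all patients could mean all those enrolled. The 8 patients per registrar match the 8 assessments in section 9.3, which for the intervention arm follow training, and section 7 starts assessments at week 6 for every registrar. The Appendix A flow chart, not shown in the text available, may also give the start of patient outcomes.

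Much of this stands. It makes the assessed-operations reading the likely one and dilution a possibility only. A reader might infer that the intervention arm will be diluted by 15% to 23%, with a definite loss of power. The documents do not support that: they give no early operating volume and no effect size, and they do not say that early patients will be analysed with the arms.

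The reply does not remove the conflict. No section ties patient outcomes to the assessed operations. The before/after analysis in section 11 needs operations that the lay summary's start rule leaves out. The control arm's start for patient outcomes is stated nowhere in the text.

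**Conclusion.** The inconsistency is established from the text and depends on no assumption: section 6 gives all patients with no start, the lay summary and synopsis give 8 per registrar after training, and section 11 does not choose between them. The consequence is conditional. On the assumptions in step 4 of the working, up to 15% (4-week course) to 23% (6-week course) of registrar-led operations would be pre-training, and the expected arm difference would shrink to as little as 85% or 77% of its full size. It would hardly shrink if registrars lead few early cases, and not at all if the set is the assessed operations. No power loss can be claimed as a finding. The point should be settled before analysis because it governs all patient outcomes under the primary objective and is cheap to settle.

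**What to change.** In sections 2, 3, 6 and 11, define one patient set for the between-arm comparison: eligible, consented patients whose THR was performed by the registrar as lead surgeon from the week-6 point already used in section 7, identically in both arms. State that these are the patients of the assessed operations, planned at 8 per registrar: 12 × 8 = 96 to 16 × 8 = 128 in total. Give 8 as the planned number rather than a cap, since section 7 makes it a minimum.

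Keep operations before week 6 out of the between-arm comparison in both arms. Retain those of the intervention registrars, labelled for the section 11 before/after analysis only. Use further patients after week 6, from operations that were not assessed, in a sensitivity analysis. Sections 7 and 9.3 together imply that training is complete by week 6; say so, because the rule relies on it.

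The cost is protocol and SAP wording, with no additional recruitment. The small downside is that some collected patients leave the main comparison.

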11 STATISTICS AND ANALYSIS

Analysis of motion data.

Motion data from the wireless sensors produces performance surrogate markers such as: the number of movements (major & minor); total path length; and smoothness/economy of movement. Data distributions will be assessed for normality using the Shapiro-Wilk test. Previous studies show such data are not normally distributed, and we would expect to use non-parametric tests, such as the Mann-Whitney U test to compare the performance metrics between the 2 groups of participants (StR's against Experts & Fellows). The Mann-Whitney U test will also be used to compare performance metrics between the two sub-groups of StR's (control and intervention), and also within the intervention sub-group in order to compare performance before and after training.

Performance metrics within all groups of participants will be reported using descriptive statistics to outline the central tendency (mean, median, and mode) and variation (range, variance, and standard deviation) in readings obtained. The Kruskal-Wallis one-way analysis of variance (ANOVA) test will be used to test for differences in the mean values obtained for all performance metrics between the two groups of participants. The Wilcoxon signed-rank test will be used to determine any differences in performance metric between the two groups.

Analysis of other routinely obtained data

X-ray (radiograph) analysis:

X-rays will be reviewed by two independent Consultant Orthopaedic Surgeons who will be blinded to the patient and lead surgeon's identity in order to reduce bias. There are several important parameters to be evaluated when reviewing a pelvic x-ray, therefore we will ask each reviewer to allocate a categorical global rating (see below) for both the pre- and post-operative x-rays. [5] The Chi-squared test will be used

to determine if there are any significant differences between each group, and also intra-group differences (for example StR's before and after additional training).

Pre-operative x-ray

- 1: Hip osteoarthritis without significant bone loss.
- 2a: Hip osteoarthritis with significant bone loss on acetabular side.
- 2b: Hip osteoarthritis with significant bone loss on femoral side.
- 3: Hip osteoarthritis with significant bone loss on both acetabular and femoral sides.

Post-operative x-ray

- 1: Excellent implant position and restoration of hip anatomy.
- 2a): Good overall with minor imperfections on acetabular side.

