12 DATA MANAGEMENT

Within this study both patients and participants will have all of their personal data anonymised via the use of Unique Patient or Participant Identifiers (UPI's). A master list of key linking identifiers for both patients

and participants will be kept on a password protected file on the OUH secure Trust Network Server. Only completely anonymised data will be used outside of OUH Trust property, which will be kept on a password-protected University owned laptop or hard-drive. We plan on keeping study data for a period of 5 years following completion on the study (up to December 2026), before securely disposing of it. We believe that this storage is appropriate as the core content is scientific research data and is therefore in the public interest. Furthermore, we will require access to this data in the case of individuals wishing to scrutinise the scientific methodology, results, or conclusions of our study.

Intra-Operative Data

Raw data will be produced from the wireless sensors. Please see section 12.3 for further details regarding the recording, transfer, and storage of this data.

Other 'personal data'

1) Electronic Patient Record Data

The following data will be obtained from the NHS Electronic Patient Records (EPR), which includes the Insignia Picture Archiving and Communication System (PACS), and the Theatre Management System (TMS):

- X-ray (radiograph) analysis.
- Theatre time usage.
- Blood test & transfusion rate analysis.
- Peri-operative morbidity (30 day).
- In-patient length of stay.
- Patient demographics (age, gender, BMI)

2) Questionnaire Data

Patient Questionnaire Data

The patient questionnaires consist of the following components:

- Patient Reported Outcome Measures: The OHS and EQ-5D.

Participant (Medical Health Professionals) Questionnaire Data

Written assessments of intra-operative performance will be conducted shortly after completion of a recorded THR. These assessments may include: Global Rating Scales (GRS), Objective Structured Assessment of Technical Skills (OSATS), and surgical checklists. The data collected from these will be anonymised as it will be linked with the UPI, and not provide any names or other personal information. The hard copies will be transcribed into digital format as soon as possible, which will be stored onto a password protected encrypted file on a University owned computer/hard-drive. The hard copies of the forms will then be disposed of.

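### Section 11 plans no analysis of whether motion metrics relate to patient outcomes, and it addresses the experience half of the same secondary objective only through surgeon grade

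*Combined protocol and SAP*

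**What the plan says.** The objective is stated in the synopsis (section 3) and in section 6, as "To determine if operative surgeon performance metrics during a THR relate to surgical experience, or patient outcomes". It returns as the third aim in section 5. The lay summary (section 2) words it as a correlation: to "determine if operative surgeon performance metrics during a THR are correlated with surgical experience, or patient outcomes".

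The analysis is described differently. The lay summary says it is "specifically aiming to identify any significant differences in either surgeon performance metrics, or patient outcome measures between" two pairs of groups: simulation-trained versus routinely trained registrars (StRs), and Trainees versus Experts. Section 11 follows that line. For the motion data, the first test named is a Mann-Whitney U test to "compare the performance metrics between the 2 groups of participants", meaning StRs against Experts and Fellows.

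On experience, the lay summary has surgeons "divided into 2 groups depending upon their position and seniority", and adds that "A sub-group analysis may be performed within the 'Expert' group also to determine any differences between the Consultants and Fellows". Section 12 lists "Patient demographics (age, gender, BMI") but no characteristic of the surgeon. Section 12.4 adds none.

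**The concern.** A comparison of groups on motion metrics, plus a separate comparison of the same groups on patient outcomes, does not show whether the two are related. StRs and Consultants could differ in path length and also in length of stay while, within each grade, path length says nothing about stay. Equally, a real relation within grades could exist when the group averages do not differ.

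This matters beyond one secondary objective. Section 11 treats the motion metrics as surrogate markers of performance. Section 5 intends an expert benchmark and recommendations to a national training committee. Whether the metrics track anything that patients experience bears directly on the value of that benchmark, and the plan as written yields no estimate of it.

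For experience, section 8.1 admits every StR with a national training number on a relevant placement and sets no limit on training year. Grade alone leaves any variation in experience among the 12-16 StRs unused.

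**Working it through.** **1. What each part of section 11 compares**

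| Data | Tests named | Contrast |
|---|---|---|
| Motion metrics | Mann-Whitney U, Kruskal-Wallis, Wilcoxon signed-rank | StRs v Experts and Fellows; control v intervention; before v after training |
| X-ray global ratings | Chi-squared | Between groups; before v after training |
| Cup inclination and version | As for motion data | Same contrasts |
| Theatre time, haemoglobin, length of stay, PROMs | t-test or Mann-Whitney U | Same contrasts |
| Transfusion, peri-operative morbidity | Chi-squared or Fisher's exact | Between groups |

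In every row the explanatory variable is a group label or a time point. No row has a motion metric on one side and a patient outcome on the other.

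**2. What is collected.** Sections 6 and 7 have StRs assessed at a minimum of 8 operations and Group 2 at a minimum of 5. Patient outcomes are collected for THRs led by any participant. Section 12.5 says motion data can be matched to other metrics of the surgery by identifier, and section 12 gives patients identifiers as well. The ingredients for an association analysis are therefore present.

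**3. Planned number (section 3).** 16 × 8 + 8 × 5 + 5 × 5 = 128 + 40 + 25 = 193 patients, which reproduces the stated total. Surgeons: 16 + 8 + 5 = 29. At the low end of recruitment in section 8.1 (12 StRs, 6 Fellows), with 5 Consultants: 96 + 30 + 25 = 151 operations by 23 surgeons.

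**4. What those numbers could detect.** The documents give no alpha, power or ICC. Assume two-sided 5%, 80% power and an ICC from 0 to 0.5.

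- Size-weighted mean cluster: m = Σm²/Σm = (16 × 64 + 13 × 25)/193 = 1349/193 = 6.99. At low recruitment: (12 × 64 + 11 × 25)/151 = 1043/151 = 6.91.
- Effective n = N/[1 + (m − 1) × ICC].
- Detectable r = tanh[(1.960 + 0.842)/√(effective n − 3)].

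Example at ICC 0.5: design effect 1 + 5.99 × 0.5 = 3.99; effective n = 193/3.99 = 48.3; r = tanh(2.802/√45.3) = 0.39.

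| ICC (assumed) | Effective n, 193 operations | Detectable r | Effective n, 151 operations | Detectable r |
|---|---|---|---|---|
| 0 | 193.0 | 0.20 | 151.0 | 0.23 |
| 0.1 | 120.7 | 0.25 | 94.9 | 0.28 |
| 0.3 | 69.0 | 0.33 | 54.5 | 0.37 |
| 0.5 | 48.3 | 0.39 | 38.2 | 0.44 |

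With one mean per surgeon, n = 29 gives r = tanh(2.802/√26) = 0.50, and n = 23 gives 0.56.

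These are figures for a simple correlation with a reduced n. They are not the power of the adjusted model proposed below. They show only that an association analysis on the planned data would be informative for moderate relations and weak for small ones.

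**The case against.** The strongest reply is that experience is captured. Grade is known for every surgeon, and section 5 defines Group 2 as post-CCT and places Fellows between StRs and Consultants. Section 11 tests StRs against Experts and Fellows on the motion metrics, and the Consultant v Fellow split is available as an option. That stands. A reader might infer from section 12 that surgeon experience is not recorded at all, but the documents do not support this. What is absent from the listed data items is a measure within grade. The fields of the participant forms named in section 12.4 are not shown, so *not listed* is as far as one can go.

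A reader might also infer that the patient-outcome question cannot be answered, or that the missing experience measure is the reason. Neither follows. Metrics and outcomes are both to be collected and can be linked. The gap is an analysis that was not specified, and it would remain even if training year were recorded.

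A third tempting inference is that an imbalance in ability between the small randomised arms could be neither seen nor adjusted for. Sections 9.2 and 9.6 give all StRs a baseline multiple-choice test and a simulated procedure, so such an imbalance could be seen. Section 11 does not say that the scores will be used for adjustment, but they exist.

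Finally, 193 is an estimate, not a ceiling. The assessment counts are minimums, recruitment may fall short, and motion recording stops if the Consultant takes over completely (section 9.7). This limits the precision figures but not the finding about section 11.

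**Conclusion.** The point holds in this form: no analysis in section 11 addresses whether performance metrics relate to patient outcomes, although the synopsis and sections 2, 5 and 6 all pose that question. Followed exactly, the plan produces no estimate for that half of the objective. The experience half is addressed, but only by grade.

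This rests on reading section 11 against the stated objective and needs no assumption. The study flow chart in Appendix A is not shown in the text available and is not held against the plan. The size is illustrative: a detectable correlation of about 0.20 to 0.39 with about 193 operations, 0.23 to 0.44 with about 151, and 0.50 to 0.56 at surgeon level, all under an assumed ICC, alpha and power. It is a gap in a secondary objective, worth closing before the data are analysed. With several metrics and many outcomes, associations chosen afterwards would be hard to interpret.

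**What to change.** In section 11:

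- Pre-specify an operation-level model of one named patient outcome on one named motion metric, with a surgeon random effect and terms for surgeon group and hospital.
- Add case-mix covariates already collected: age, BMI, pre-operative X-ray grade and, for PROMs, the baseline score. Without them, a harder hip could both lengthen the operation and worsen the outcome.
- Label all other metric-outcome pairs exploratory. Fit one metric per model, since path length, movements and time are likely to be collinear. Keep sparse binary outcomes (transfusion, morbidity) descriptive.
- State the key that links each motion record to its patient.

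For experience, record at consent each surgeon's training year (or years since CCT) and number of previous THRs as lead. Report a surgeon-level rank correlation of the mean metric with previous THR count.

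Adjusting the randomised StR comparison for experience or for the baseline skills score is optional.

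Cost: two questions per surgeon, one pre-specified model and one rank correlation, with no extra visit or patient. The optional adjustment spends one degree of freedom with 12-16 StRs.
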